According to an expert consensus on best practices for post-acute rehabilitation after THA and TKA, rehabilitation should start within 3 weeks of discharge ¹⁰. Despite the absence of criteria on specific dose parameters of duration, frequency, and number of treatment sessions, the recommendations support 4 to 12 weeks of supervised rehabilitation, 2 to 3 times per week ¹⁰. There is also evidence stating that therapeutic exercise should be a primary component of post-operative care, and that the exercise programs should be supervised and progressed as the patients meet clinical and strength milestones ^{9,13}.

Regarding the rehabilitation setting, home-based and clinic-based rehabilitation protocols have generated similar improvements ^{7,19-24}. Also, tele-rehabilitation has demonstrated similar outcomes in comparison to standard rehabilitation ^{21,22,25}.

These findings are in line with recent trends in healthcare delivery, away from inpatient care and towards home-based care, towards cost-effectiveness improvement. Optimizing uptake and adherence is of paramount importance ²⁶, and this can be maximized by home-based care ²⁷.

In this sense, digital health solutions that empower patients, maximize engagement and allow home-based rehabilitation, without the need for constant therapist supervision, could improve effectiveness and lower the cost of rehabilitation.

Hence, we created SWORD Phoenix, a novel digital biofeedback system for home-based physical rehabilitation. SWORD Phoenix® is a class I medical device that, using inertial motion trackers, digitizes patient motion and provides real-time feedback on performance through a mobile app. It also includes a web-based platform that allows the clinical team to prescribe, monitor and adapt the rehabilitation process remotely. This way, the system allows patients to perform independent rehabilitation sessions at home without the need for constant therapist supervision, ensuring remote monitoring throughout the rehabilitation program.

The efficacy of SWORD Phoenix has already been demonstrated in two previous feasibility studies conducted at Hospital da Prelada, Porto, Portugal, between December 2016 and March 2018 (Clinical trial IDs: NCT03047252 and NCT03045549). These were two parallel-group studies, comparing the clinical evolution of patients submitted to an 8-week rehabilitation program after THA or TKA, divided into two distinct groups: the experimental group, which performed a home-based rehabilitation program using SWORD Phoenix, and the control group, which was also engaged in a home-based rehabilitation program, but with conventional physiotherapy instead. Geographical location was used as the allocation criterion, with patients living within the city's administrative limits allocated to the conventional physiotherapy group and patients living outside the city's administrative limits allocated to the experimental group. Results from the experimental group were superior to those from the conventional physiotherapy group in all outcome measures, and adverse effects rates were similar in both groups. The main results of the TKA study were already published ²⁸, and the main results of the THA study are in publication route.

More recently, a new version of the system was developed, where the possibility to execute bilateral exercises was added, focusing not only on the rehabilitation of the affected limb, but also on muscular reinforcement of the contralateral limb. As such,

a new clinical study was designed, aiming at exploring the clinical impact of this update on the therapeutic program (bilateral).

The present study is a single-center, prospective, single-arm, historical control study, designed to evaluate the clinical outcomes of a bilateral home-based rehabilitation program using **SWORD Phoenix®**. The clinical outcomes will be compared to those of the above-mentioned feasibility studies. The investigation hypothesis is that the clinical outcomes of the bilateral exercise program will be superior to those of the unilateral exercise program.

2. Study Outcomes

The aim of the studies is to evaluate the clinical impact of a home-based bilateral rehabilitation program after THA or TKA, using **SWORD Phoenix®**.

a) Primary outcome

The primary outcome will be the change in patient performance compared to the baseline, measured through the TUG.

b) Secondary outcomes

- The change in patient reported outcomes, measured by HOOS and KOOS scales, as compared to baseline evaluation
- The change in the maximum amplitude of joints movements, as compared to baseline evaluation

3. Sample size estimate

Sample size estimation calculations were performed taking into consideration the primary outcome measure - Timed up and Go (TUG) test score. Calculations were based on the baseline TUG distribution of the participants in the two previous feasibility studies (total n=131; mean 18,00 seconds; sd=6,3) and on a Minimal Clinical Significant Change of 2.27 seconds as reported by Yuksel *et al.*²⁹.

Considering a power of 80%, a two-sided 0.05 significance level and an allocation rate of 2:1, 216 patients (144 in this study; 72 historical control) would be necessary to detect a 2.27 seconds difference against the historical control.

4. Inclusion criteria

- a) Patients over 18 years old
- b) Clinical and imaging evidence of hip/knee osteoarthritis
- c) Indication for total hip or knee replacement according to the patient's orthopedic surgeon
- d) Ability to walk unaided, with unilateral or bilateral support
- e) Availability of a caregiver to assist the patient after surgery

5. Exclusion criteria

- a) Patients admitted for revision of total hip/knee replacement
- b) Contralateral hip or knee osteoarthritis severely limiting patient mobility and ability to comply with a rehabilitation program
- c) Aphasia, dementia or psychiatric comorbidity interfering with the communication or compliance to the rehabilitation process
- d) Respiratory, cardiac, metabolic or other condition incompatible with at least 30 minutes of light to moderate physical activity
- e) Major medical complications occurring after surgery that prevent the discharge of the patient within 10 days after the surgery
- f) Other medical and/or surgical complications that prevent the patient from complying with a rehabilitation program
- g) Blind and/or illiterate patients
- h) Patients residing outside a 30km radius from the investigation center

6. Methods for identifying and recruiting patients

All patients admitted for total hip or knee replacement during the study period will

be screened for inclusion and exclusion criteria.

When a potential candidate is identified, the local investigator will approach the candidate and explain the study in detail. The prospective candidate will be given the patient information document and sufficient time to consider whether he wishes to participate in the study.

Subsequently, the prospective candidate will be given opportunity to clarify any doubts, after which the informed consent form will be signed and dated in duplicate by the patient and the investigator. Only then will the randomization and baseline assessments be performed.

7. Informed consent

Informed consent will be delivered in paper format (see annex), informing individuals of their free will to drop out of the study, without any prejudice to their health assistance or medical attention. It includes information on collected data confidentiality and its publication potential in scientific journals, respecting all due ethical standards.

Finally, it assures the individual that he was correctly informed about the study, requiring the signature from both the patient and one of the study researchers.

8. Data anonymization

Numerical codes will be attributed to each study participant. As soon as possible, all the information from the questionnaires will be transferred to digital data bases and the documents kept in a specific location at SWORD Health, SA headquarters, with restricted access.

9. Scales and assessment tools

Several studies suggest that the outcomes should be measured not only in terms of range of motion, which is considered a poor marker of implant success and patient satisfaction^{9,30-32} but also using patient-reported outcomes and a performance test^{33,34}. As such, results will be evaluated according to three outcome measures: **a)** a performance test; **b)** patient-reported outcomes (using HOOS and KOOS scales); **c)**

range of motion of the hip or knee.

a) Performance test

Timed up and Go (TUG) test was selected as a performance test, which measures the time the patient takes to rise up from a chair, walk three meters, turn around, walk again towards the chair and sit. This test was chosen as it is simple and practical, quick and easy to administer, has high inter-rater reliability ³⁵ and has been demonstrated to predict both short- ³⁶ and long-term ^{37,38} function, following arthroplasty.

Instructions to perform the test:

- 1) Select a chair with armrests and a seating height of 44-47 cm
- 2) Measure 3 meters in a straight line from the chair and place a mark on the floor
- 3) Ask the patient to sit in a chair with his/her back against the chair back
- 4) Instruct the patient to rise from the chair on the command “go”, walk 3 meters at a comfortable and safe pace, turn, walk back to the chair and sit down
- 5) Begin timing at “go” and stop when the patient is seated
- 6) Register the time with two decimal digits in the patient file

b) Patient reported outcomes scales

b.1. Hip Osteoarthritis Outcome Scale (HOOS)

The HOOS scale was validated for patients submitted to THA by Nilsson and colleagues ³⁹. The HOOS consists of 5 subscales: 1) Pain; 2) other Symptoms; 3) Function in daily living (ADL); 4) Function in sport and recreation (Sport/Rec) and 5) hip related Quality of life (QOL). The previous week is the time period considered when answering the questions. Standardized options are given and each question is assigned a score from 0 to 4 (5 Likert boxes). A normalized score (100 indicating no symptoms and 0 indicating extreme symptoms) is calculated for each subscale.

A copy of the questionnaire can be found in each patient file. To administer the questionnaire sheet, the investigator must extract it from the study file and hand it over to the patient, so he can fill in the form. The patient cannot be assisted in performing the movement at any time. Once finished, the sheet must be signed and dated by the investigator, and archived in the patient file.

b.2. Knee Osteoarthritis Outcome Score (KOOS)

The KOOS scale ⁴⁰ was validated for patients submitted to TKA by Alviar and colleagues ⁴¹. The KOOS consists of 5 subscales: 1) Pain; 2) other Symptoms; 3) Function in daily living (ADL); 4) Function in sport and recreation (Sport/Rec) and 5) knee related Quality of life (QOL). The previous week is the time period considered when answering the questions. Standardized options are given and each question is assigned a score from 0 to 4. A normalized score (100 indicating no symptoms and 0 indicating extreme symptoms) is calculated for each subscale.

A copy of the questionnaire can be found in each patient file. To administer the questionnaire sheet, the investigator must extract it from the study file and hand it over to the patient, so he can fill in the form. The patient cannot be assisted in performing the movement at any time. Once finished, the sheet must be signed and dated by the investigator, and archived in the patient file.

c) Range of motion of the hip and knee

Hip and knee range of motion will be assessed based in three distinct positions: lying, sitting and standing. The system used in the study is a validated medical device for joint angle measurement. Therefore, knee range of motion will be measured automatically by the system.

In this study, the active range of motion will be measured through the following movements:

| Knee: | Hip: |
|------------------------|-----------------------------|
| Lying knee flexion | Lying hip flexion |
| Sitting knee flexion | Lying hip abduction |
| Standing knee flexion | Standing hip flexion |
| Sitting knee extension | Standing hip abduction |
| | Standing hip hyperextension |

To assess range of motion, the investigator will need to:

- 1) Create a patient profile in the Portal
- 2) Prescribe one set of each exercise, with 5 repetitions
- 3) Ask the patient to perform the session through the App, executing each repetition to the best of his ability
- 4) After the session, login to the Portal, go to the session's results and click on detailed results for each exercise. Record the flexion or extension angle of the best repetition for each exercise in the patient file.

10. Patient assessment

Patients will be assessed at baseline (pre-operatively) (A1), upon discharge (A2), at 4 weeks after rehabilitation program initiation (A3), and at the end of it (A4).

Assessments will be performed within a time window of 5-working-days, previous or ahead of the day the assessment was scheduled for.

Baseline assessment (A1)

Participant characterization will consist of:

- Demographics (gender, age at enrollment);
- Educational level (years at school);
- Diagnosis and affected side
- Date of surgery

- Height, weight, body Mass Index
- Comorbidities
 - Smoking
 - Diabetes
 - Cardiac disease
 - Respiratory disease
 - Hypertension
 - Stroke
 - Renal Disease
 - Bleeding disorders
 - Previous hip/knee replacement
 - American Society of Anesthesiologists physical status classification score of 3 or 4⁴²

b) HOOS/KOOS score

c) Timed Up and Go (TUG) test score

d) Hip and knee active range of motion

Assessment upon discharge (A2)

Patients will be reevaluated immediately upon hospital discharge, and the following parameters will be registered:

- Surgery date
- Operative time
- Type of prosthesis
- Adverse effects before discharge

Subsequent assessments (A3 e A4)

Patients will be reassessed at 4 and 8 weeks after rehabilitation program initiation, collecting the following data:

- TUG score
- HOOS / KOOS score
- Maximum range of motion of the affected joint

11. Intervention

Upon hospital discharge, all participants will have immediate access to home-based rehabilitation therapy.

The rehabilitation program will be carried out at home, using **SWORD Phoenix®**. Patients will be instructed to engage on their rehabilitation sessions daily, but will not be excluded from the study in case this periodicity is not respected.

The rehabilitation programs proposed are presented in **Tables 1 to 4**.

Table 1: Hip replacement rehabilitation protocol - Stage 1 (weeks 0-5)

| Stage 1 (weeks 0-4) | |
|--|--|
| Objectives | Precautions |
| Decrease pain and swelling | Avoid hip internal rotation and hip adduction beyond neutral |
| Restore range of motion | Avoid hip flexion above 90° |
| Strengthen hip flexors and abductors | Ice pack application after each session and throughout the day as needed |
| Restore full load capacity on both legs | |
| Intervention | |
| Open kinetic chain exercises without added resistance | |
| Lying: 
 - Bilateral Hip Flexion (1x20-24 reps) - Operated Limb Hip Flexion (1x12-14 reps) - Bilateral Hip Abduction (1x20-24 reps) - Operated Limb Hip abduction (1x20-24 reps) - Bilateral Knee flexion (1x20-24 reps) - Operated Limb Knee Flexion (1x12-14) | |
| Standing (initially with support) 
 - Bilateral Hip Flexion (1x20-24 reps) - Operated Limb Hip Flexion (1x12-14 reps) - Bilateral Hip Abduction (1x20-24 reps) - Operated Limb Hip abduction (1x12-14 reps) - Bilateral Knee flexion (1x20-24 reps) - Operated Limb Knee Flexion (1x12-14 reps) - Bilateral Hip Flexion with Knee Flexion (1x20-24) - Operated Limb Hip flexion with knee flexion (1x12-14 reps) - Bilateral Hip hyperextension (1x20-24 reps) - Operated Limb Hip Hyperextension (1x12-14 reps) | |
| Closed kinetic chain exercises | |
| 
 - Bridge (2x12-14) - Squats (2x12-14 reps) | |
| Note 1: adjust sets, reps and total session duration according to patient tolerance (based on patient performance and on the pain and fatigue scores attributed by the patient at the end of each session) | |

Note 2: aim for at least 30 minutes in total

Note 3: recommend two daily sessions as soon as tolerated

Table 2: Hip replacement rehabilitation protocol - Stage 2 (weeks 6-8)

| Stage 2 (weeks 5-8) | |
|--|----------------------|
| Objectives | Precautions |
| 
Strengthening of hip flexors and abductors
 
Improve balance
 
Independence on all activities of daily living
 | Identical to stage 1 |
| Intervention | |
| 
Open kinetic chain exercises in the lying, sitting and standing positions
 
Lying:
 
 - Bilateral Hip Flexion (1x26-30 reps) - Operated Limb Hip Flexion (1x17-20 reps) - Bilateral Hip Abduction (1x26-30 reps) - Operated Limb Hip abduction (1x17-20 reps) - Bilateral Knee flexion (1x26-30 reps) - Operated Limb Knee Flexion (1x17-20 reps) - Bilateral Hip Flexion with Knee Flexion (1x26-30 reps) - Operated Limb Hip flexion with knee flexion (1x17-20 reps) 
Standing
 
 - Bilateral Hip Flexion (1x26-30 reps) - Operated Limb Hip Flexion (1x17-20 reps) - Bilateral Hip Abduction (1x26-30 reps) - Operated Limb Hip abduction (1x17-20 reps) - Bilateral Knee flexion (1x26-30 reps) - Operated Limb Knee Flexion (1x17-20 reps) - Bilateral Hip Flexion with Knee Flexion (1x26-30 reps) - Operated Limb Hip flexion with knee flexion (1x17-20 reps) - Bilateral Hip hyperextension (1x26-30 reps) - Operated Limb Hip Hyperextension (1x17-20 reps) 
Closed kinetic chain exercises
 
 - Bridge (2x17-20 reps) - Squats (2x17-20 reps) - Bilateral Stand to Sit (2x12 reps) - Bilateral Wall Sit (2x15-30 secs) 
Functional exercises
 
 - Bilateral Forward Lunge (1x20-24 reps) - Operated Limb Forward Lunge (1x12-14 reps) | |

SH-SA-THKR-01 Study Protocol

- Bilateral Climb a Step (1x20-24reps)
- Operated Limb Climb a Step (1x12-14 reps)
- Bilateral Come down a Step (1x20-24reps)
- Operated Limb Come down a Step (1x12-14 reps)

Note 1: adjust sets, reps and total session duration according to patient tolerance (based on patient performance and on the pain and fatigue scores attributed by the patient at the end of each session)

Note 2: maintain recommendation of two sessions/day

Table 3: Knee replacement rehabilitation protocol - Stage 1 (weeks 0-4)

| Stage 1 (weeks 0-4) | |
|--|--|
| Objectives | Precautions |
| Decrease pain and swelling Gain range of motion | Beware with the tissues on the surgical wound |
| Strengthen knee extensors and flexors Restore fully load capacity on both legs | Ice pack application after each session and throughout the day as needed |
| Intervention | |
| Recommendations of good practices on the TKR procedure on the deploy day | |
| Open kinetic chain exercises without added resistance | |
| Lying | |
| 
 - Bilateral Hip Flexion (1x20-24 reps) - Operated Limb Hip Flexion (1x12-14 reps) - Bilateral Hip Abduction (1x20-24 reps) - Operated Limb Hip abduction (1x12-14 reps) - Bilateral Knee flexion (1x20-24 reps) - Operated Limb Knee Flexion (1x12-14 reps) - Lateral decubitus Hip Abduction (2x10-12 reps) - Clamshells (2x10-12 reps) - Bridge (2x10-12 reps) | |
| Sitting | |
| 
 - Bilateral Knee Flexion (1x20-24 reps) - Operated Limb Knee flexion (1x12-14 reps) - Bilateral Knee Extension (1x20-24 reps) - Operated Limb Knee extension (1x12-14 reps) | |
| Standing (initially with support) | |
| 
 - Hip abduction (2x10 reps) - Hip hyperextension (2x10 reps) - Knee flexion (2x10 reps) - Hip flexion with knee flexion (2x10 reps) | |
| Closed kinetic chain | |
| 
 - Mini-squats (2x10 reps) - Bridge (2x10 reps) | |

Note 1: adjust sets, reps and total session duration according to patient tolerance based on the pain and fatigue attributed (aim for at least 30 minutes in total)

Note 2: recommend two daily sessions as soon as tolerated

Table 4: Knee replacement rehabilitation protocol - Stage 2 (weeks 5-8)

| Stage 2 (weeks 5 - 8) | |
|--|-----------------|
| Objectives | Precautions |
| Strengthening of knee flexors and extensors Increase active range of motion Improve balance Independence on all activities of daily living | Same as stage 1 |
| Intervention | |
| Open kinetic chain exercises in the lying, sitting and standing positions: | |
| Lying: 
 - Bilateral Hip Flexion (1x26-30 reps) - Operated Limb Hip Flexion (1x17-20 reps) - Bilateral Hip Abduction (1x26-30 reps) - Operated Limb Hip abduction (1x17-20 reps) - Bilateral Knee flexion (1x26-30 reps) - Operated Limb Knee Flexion (1x17-20 reps) - Lateral decubitus Hip Abduction (2x15-20 reps) - Clamshells (2x15-20 reps) | |
| Sitting 
 - Bilateral Knee Flexion (1x26-30 reps) - Operated Limb Knee flexion (1x17-20 reps) - Bilateral Knee Extension (1x26-30 reps) - Operated Limb Knee extension (1x17-20 reps) | |
| Standing 
 - Bilateral Hip Flexion (1x26-30 reps) - Operated Limb Hip Flexion (1x17-20 reps) - Bilateral Hip Abduction (1x26-30 reps) - Operated Limb Hip abduction (1x17-20 reps) - Bilateral Knee flexion (1x26-30 reps) - Operated Limb Knee Flexion (1x17-20 reps) - Bilateral Hip hyperextension (1x26-30 reps) - Operated Limb Hip Hyperextension (1x17-20 reps) | |
| Closed kinetic chain exercises | |
| 
 - Bridge (2x17-20 reps) - Squats (2x17-20 reps) - Bilateral Stand to Sit (2x12 reps) - Bilateral Wall Sit (2x15-30 secs) | |

Functional exercises

- Bilateral Climb a Step (1x20-24reps)
- Operated Limb Climb a Step (1x12-14 reps)
- Bilateral Come down a Step (1x20-24reps)
- Operated Limb Come down a Step (1x12-14 reps)

Note 1: adjust sets, reps and total session duration according to patient tolerance based on the pain and fatigue attributed (aim for at least 45 minutes in total)

Note 2: maintain recommendation of two sessions/day

In any case, these protocols can be tailored to the patient's specific needs, according to the joint assessment between the orthopedic surgeon and the physical therapist.

The rehabilitation process will be remotely accompanied by SWORD Health clinical team, with phone calls and home visits to the patient whenever needed.

12. Home visits

Each of the participants will be assigned a physiotherapist, who will pay an initial visit to teach the patient how to operate the system, as well as to prescribe an exercise program based on the presented guidelines and adapted to the patient's specific needs. The therapist will perform an initial session with the patient, ensuring that the patient is able to perform each exercise and that he can operate the system, alone or with the help of a caregiver.

From here on, the patient will be followed remotely by the physiotherapist, with no home sessions. On the 4th week of therapy, each participant will receive an interim visit, in which the therapist will assess patient progress and adjust the rehabilitation program accordingly. This visit will not consist of a face-to-face session.

Additionally, a progress assessment phone call will be performed every two weeks (at weeks 2 and 6).

Extraordinary visits or phone call may be performed in case of necessity. Whenever it happens, these events will be recorded on patient's file (date, occurrence, duration)

13. Safety and adverse events

Patient safety will be ensured at all times during the sessions, and will be evaluated through pain and fatigue scores (graduated from 0 to 10) collected at the end of each session. These will be presented to the patient using the mobile App and will be available for remote monitoring by their physical therapist. In case of excessive pain or fatigue, patients will be contacted by their physical therapist to ascertain the cause and change prescription. Patients will also be asked to report any other adverse events to their physical therapist by telephone, and these will be registered on the patient's file (date of the event, date of resolution - if applicable, resolution

state, gravity).

14.Risks and Benefits to Participants

All participant will benefit from therapeutic rehabilitation immediately upon hospital discharge. Thus, the access to rehabilitation care is assured, which will likely translate into potential benefits for the patient. Patients will engage in a home-based rehabilitation program through **SWORD Phoenix®**, according to the latest treatment guidelines and following the clinician's recommendations. A physiotherapist will be allocated to each patient, guaranteeing a continuous follow up and home visits whenever necessary. Since the system will be used in line with its certified therapeutic indications, there will be no added risk or inconvenient to the user. In fact, the rate of adverse events reported on previous clinical trials was identical to that reported with conventional physiotherapy. Hence, participants are not exposed to any added risk, being able instead to directly benefit from a breakthrough technology, that allows a real and immediate measure of their performance, increasing their motivation and maximizing rehabilitation outcomes even further.

15.Results analysis

Per-protocol and intention-to-treat analysis will be applied to evaluate the study outcomes. Participants with an adhesion rate below 43% (corresponding to less than 3 sessions per week) will not be considered in the per-protocol analysis.

Intervention's impact on primary and secondary outcomes will be performed considering the variables evolution when comparing basal assessment and assessment at 8 weeks.

16.Confidentiality of Personal Data

Data collection for this study was authorized by the National Commission on Data Protection, with the authorization number 1476/2017.

Personal data will only be accessible to authorized individuals in this study. Personal data will not be entered into the database as part of this research. The clinical data

collected will only be linked to the patient by a unique study number and will contain no personal identifiers. Informed consent will be obtained from participants to collect and retain this data. The data that will be used for analysis and dissemination for research purposes will be completely anonymized.

17. Ethical issues

All participants will be provided with information about the purpose and procedures of the study and gave written informed consent before inclusion.

The study was approved by the local ethics committee (Chair: [name] [name]) and will be conducted in accordance with the relevant guidelines and regulations.

18. System technical specifications

SWORD Phoenix® system is composed of the following three interconnected components:

Motion trackers

The motion trackers are placed on body segments using Velcro® straps. Each motion tracker is placed in a specific position. To assist in the correct placement of the motion trackers, both the trackers and the matching straps are color-coded. In this study, the following setup will be used:

- **Red tracker:** over the sternal manubrium
- **Green trackers:** on the lateral surface of the leg, approximately midway between the trochanter and the lateral epicondyle
- **Blue trackers:** on the upper third of the antero-medial surface of the tibia

Mobile App

The mobile app guides the patient in each exercise session. Before each exercise, the patient is presented with a real-life video and audio explanation of that exercise. The execution interface is subsequently shown. This screen features: a) a progress bar; b) a repetition counter; c) a star counter and d) a timer displaying time left in the

exercise.

A correct repetition is defined as a movement starting at the baseline and reaching or surpassing the specified target, without violating movement or posture constraints. In case the patient violates a constraint, a message is prompted showing which movement error was performed, so that the patient can correct the movement in the following attempts.

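### The historical control is never named as the earlier SWORD Phoenix arms, and section 15 gives no between-group analysis to test the stated hypothesis

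*Combined protocol and SAP*

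**What the plan says.** All references are to the combined protocol and SAP.

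- **Section 1, comparison.** After describing the two earlier studies, the introduction says "The clinical outcomes will be compared to those of the above-mentioned feasibility studies". No arm is named.
- **Section 1, earlier studies.** Each had a SWORD Phoenix arm and a conventional home physiotherapy arm, allocated by place of residence. "Results from the experimental group were superior to those from the conventional physiotherapy group in all outcome measures".
- **Section 1, hypothesis.** "The investigation hypothesis is that the clinical outcomes of the bilateral exercise program will be superior to those of the unilateral exercise program". The aim is likewise framed around the effect of the bilateral update to the device.
- **Section 3.** The SD comes from the "baseline TUG distribution of the participants in the two previous feasibility studies (total n=131; mean 18,00 seconds; sd=6,3"), with both arms pooled. The result is that "216 patients (144 in this study; 72 historical control) would be necessary to detect a 2.27 seconds difference against the historical control". The arm that supplies the 72 is not identified.
- **Section 15.** It defines intention-to-treat and per-protocol sets, a 43% adherence cut-off for the latter, and an evaluation of change from baseline to 8 weeks. It does not mention the historical control, a between-group estimate or test, covariates, or how the cut-off applies to controls.
- **Section 10.** Baseline TUG, diagnosis and comorbidities are recorded for the new cohort. The available text states no use of them in the analysis.

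**The concern.** In a single-arm study, the choice of control and the method of comparison carry the whole inference. Here a comparison is announced in section 1 and sized in section 3, but the analysis section does not carry it out.

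Three consequences follow. First, a within-cohort change after joint replacement and rehabilitation shows improvement but says nothing about bilateral against unilateral exercise. Second, a comparison with the feasibility studies as whole studies would bring in conventional patients, so part of the apparent benefit would repeat a difference already known. Third, the earlier results are already known to the sponsor. An open choice of arm, model and covariates can therefore be settled after half the data have been seen.

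**Working it through.** **1. The passages side by side.**

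| Place | Control named? | Between-group method? |
|---|---|---|
| Section 1, comparison sentence | the two studies, no arm | none |
| Section 1, aim and hypothesis | implied: unilateral Phoenix programme | none |
| Section 3 | historical control, no arm | a 2.27 s difference, two-sided 0.05 |
| Section 15 | not mentioned | none; baseline versus 8 weeks only |

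**2. Can the Phoenix arms supply 72?** That needs 72/131 = 55% of the earlier participants. Arm sizes are not given. An equal split would give about 65 (131/2 = 65.5).

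**3. The plan's own figure.** Inputs from section 3: difference 2.27 s, SD 6.3 s, 80% power, 2:1. Controls needed = (1 + 1/2) × SD² × (z_α + z_power)² / difference².

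- Two-sided 0.05: 1.5 × 39.69 × 2.8016² / 5.153 = 90.7, so 91 + 182 = 273.
- One-sided 0.05: 1.5 × 39.69 × 2.4865² / 5.153 = 71.4, so 72 + 144 = 216.

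The stated 216 matches the one-sided calculation, although section 3 says two-sided. That is a separate matter. It explains why the next table starts at 70% and not 80%.

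**4. Power by number of controls.** 144 new patients, two-sided 0.05, SD 6.3 s, no adjustment, noncentral t. SE = 6.3 × √(1/144 + 1/n).

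| Controls | SE (s) | 2.27/SE | Power |
|---|---|---|---|
| 72 (plan) | 0.909 | 2.50 | 70% |
| 65 (assumed) | 0.941 | 2.41 | 67% |
| 50 (assumed) | 1.034 | 2.20 | 59% |

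The 6.3 s is the SD of baseline TUG, not of change. If TUG has SD 6.3 s at both times and correlation ρ, the SD of change is 6.3 × √(2(1 − ρ)), and the baseline-adjusted SD is 6.3 × √(1 − ρ²). For ρ = 0.3 / 0.5 / 0.7 (assumed) and 65 controls, power is 53 / 67 / 87% unadjusted and 71 / 79 / 92% adjusted.

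**5. Why one model cannot simply be trusted.** Suppose the groups differ by 2 s at baseline and there is no true effect (144 versus 65, SD 6.3 s, same ρ values, all assumed).

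- *The difference regresses.* The change score is biased by 2 × (1 − ρ) = 1.4 / 1.0 / 0.6 s. If new patients start slower, simulation gives a false significant benefit in about 24 / 18 / 13% of trials, against a nominal 2.5%. The baseline-adjusted estimate stays near 2.5%.
- *The difference persists to 8 weeks.* The change score is unbiased (2–3%). The baseline-adjusted estimate is biased by 2 × (1 − ρ) = 1.4 / 1.0 / 0.6 s. If new patients start faster, it gives a false benefit in 33 / 23 / 14%.

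The two models fail in opposite situations, and the documents do not show which situation applies.

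**The case against.** The strongest reply is that the comparator is clear from context. The hypothesis follows directly after the comparison sentence and names the unilateral programme, which only the Phoenix arms received through the device being updated. A comparison is announced and sized. Pooling both arms for a baseline SD is ordinary practice and says nothing about who the control is. All of this stands, so the plan does intend a comparison and most likely means the Phoenix arms. What remains is that sections 3 and 15 do not fix that choice, and section 15 as written does not perform the comparison.

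Three stronger readings are tempting, and the documents do not support them.

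- A reader might infer that conventional patients will be pooled into the control. The aim and hypothesis point the other way. As an illustration only, if half of 72 controls were conventional and worse by 1 / 2.27 / 4 s, the bias would be 0.5 / 1.135 / 2.0 s and the false-benefit chance 8 / 24 / 59% at SD 6.3 s. Neither the share nor the gap is in the documents.
- A reader might infer that adjusting for baseline TUG removes the bias. Step 5 shows that this depends on an assumption that cannot be verified here. It also requires the same baseline time point. Section 10 puts the new baseline before surgery, but section 3 gives no timing for the earlier one.
- A reader might infer a residence imbalance, since the earlier Phoenix arms consisted of "patients living outside the city's administrative limits allocated to the experimental group" while this study excludes only "Patients residing outside a 30km radius from the investigation center". That holds only if the centre serves the same city, which the available text does not state.

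**Conclusion.** The point holds as a gap in specification that affects the main claim. In the available text, the comparison sentence and sections 3 and 15 do not name the control arm, and the only contrast in section 15 cannot test the stated hypothesis. Confidence in this is high, because it rests on the text alone.

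The size of any bias is unknown. The documents give no arm sizes, no gap between the earlier arms, no SD of change and no correlation between baseline and 8 weeks. The power figures of 70%, 67% and 59% rest on SD 6.3 s applied to the change. The 65 and 50 controls are assumptions. The false-benefit rates illustrate why the analysis must be chosen in advance and do not estimate what will happen. This should be corrected, and correcting it is cheap.

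**What to change.** **Control.** State in sections 1, 3 and 15 that the primary comparison is the change in TUG from baseline to 8 weeks in this cohort versus all patients in the SWORD Phoenix arms of the two feasibility studies. Exclude the conventional arms and select no control on outcome.

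**Model.** Prespecify a between-group model adjusted for joint (hip or knee) and baseline TUG, after confirming that baseline was pre-operative in both cohorts. Report the estimate without baseline adjustment beside it, both with 95% CIs. Say in advance that agreement supports the conclusion and that disagreement will be reported.

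**Eligibility and adherence.** Apply this study's criteria and the 43% rule to controls only where the records allow. Otherwise report per-protocol results for the new cohort only.

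**Reporting.** Give the actual number of controls and the resulting two-sided power. State that calendar period (controls come from studies run December 2016 to March 2018), and residence if the city is the same, remain possible confounders.

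**Cost.** Wording, some extra analysis and a check of the earlier records, with no new patients or visits. Joint follows from the separate hip and knee studies, and section 3 already summarises baseline TUG for the 131. The downsides are fewer controls than the pooled 131, possible gaps in the earlier records, and a conclusion that depends on two estimates agreeing.
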